#### **8.2.3.5. Exploratory analyses**

Additional analyses may be performed as necessary. Results of exploratory analyses will be reported only if the analyte provide important interpretation.

#### **8.2.4. Effectiveness analyses**

##### **8.2.4.1. Hematologic response**

For patients who achieved the following responses based on the best overall response of hematologic response, their proportion and its confidence interval will be determined as per Section 8.1.3. Patients who underwent no clinical assessment of hematologic response will also be included in the analysis, but another analysis in patients except them will also be performed.

- CR or CRi
- CR
- CRi

Cycles in which CR or CRi was achieved for the first time will be analyzed by determining the proportion of patients as per Section 8.1.2. The relevant cycle is determined based on the assessment date for which CR or CRi was determined and shall include the date of the most recent past dose of this drug. If the assessment date is 29 days after the last dose or later, however, the cycle should be determined to be post-treatment; the following categories will be used for this analysis.

- Cycle 1, Cycle 2, Cycle 3, Cycle 4, Cycle 5, Cycle 6, Cycle  $> 6$ , post-treatment

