8.8.11. Clinical Evaluation

8.8.11.1. Hematologic Remission

Response will be assessed according to the following response criteria, and the best overall response during the observation period will be entered. However, if subsequent treatment for the target disease is started or HSCT is performed, the best overall response before the start of the subsequent treatment or HSCT, whichever is earlier, will be entered.

Response criteria

1. CR
 - No peripheral blasts or extramedullary disease (no lymphadenopathy, splenomegaly, or skin/gum infiltration/testicular mass/CNS involvement)
 - Trilineage hematopoiesis (TLH) and <5% blasts
 - Absolute neutrophil count (ANC) >1,000/ μ L
 - Platelets >100,000/ μ L
 - No recurrence for 4 weeks
2. CRi (CR with incomplete count recovery)
 - Recovery of platelets but <100,000/ μ L or ANC is <1,000/ μ L
3. Progressive disease (PD)
 - Increase of at least 25% in the absolute number of peripheral blood or bone marrow blasts or development of extramedullary disease
4. Relapsed disease
 - Reappearance of blasts in the blood or bone marrow (>5%) or in any extramedullary site after CR
5. Inevaluable

Inotuzumab

B1931024 NON-INTERVENTIONAL STUDY PROTOCOL

Amended 8, 12 December 2023

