#### 5.2. Effectiveness Analysis Set

The effectiveness analysis set (EAS) consists of all patients in the SAS except those who meet any of the following conditions:

- h. Effectiveness cannot be appropriately evaluated because some of the necessary conditions for evaluating effectiveness are missing. (Indicated as "Unable to evaluate effectiveness" in the survey report.)
- i. Disease is outside the scope of survey. (Indicated as "Disease outside the scope" in the survey report.)  
This survey includes the following exclusion criterion: Patients whose condition is not relapsed or refractory CD22+ acute lymphocytic leukemia (ALL)

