- Peripheral blast count immediately before the start of this drug [ $\leq 1000/\mu\text{L}$ ,  $> 1000/\mu\text{L}$ , not performed]
- Myeloblast count immediately before the start of this drug [ $\leq 50\%$ ,  $> 50\%$ , not performed]
- Salvage line of the induction treatment with this drug [Initial induction, 1st, 2nd, 3rd or later]
- HSCT before the start of this drug [not performed, performed]
- Pregnancy [absent, present] \* Pregnancy during the treatment period. Limited to cases in which information on pregnancy is collected

Subgroup analyses of overall survival (OS) will be performed for the following patient characteristics and other factors:

- Age [ $< 15$  years,  $\geq 15$  to  $< 65$  years,  $\geq 65$  years]
- Age [ $< 18$  years,  $\geq 18$  to  $< 55$  years,  $\geq 55$  years]
- Age [ $< 15$  years,  $\geq 15$  to  $< 40$  years,  $\geq 40$  years]
- Disease name [Relapsed CD22+ acute lymphocytic leukemia (ALL), refractory CD22+ ALL]
- Chromosome karyotype [normal, t (4;11), unknown]
- Chromosome karyotype [Philadelphia chromosome positive, negative, unknown]\* Philadelphia chromosome is considered positive if the chromosome karyotype is t(9;22).
- Hemoglobin level immediately before the start of this drug [ $< 10\text{ g/dL}$ ,  $\geq 10\text{ g/dL}$ , not performed]
- Platelet count immediately before the start of this drug [ $< 10 \times 10^4/\mu\text{L}$ ,  $\geq 10 \times 10^4/\mu\text{L}$ , not performed]
- Peripheral blast count immediately before the start of this drug [ $\leq 1000/\mu\text{L}$ ,  $> 1000/\mu\text{L}$ , not performed]
- Myeloblast count immediately before the start of this drug [ $\leq 50\%$ ,  $> 50\%$ , not performed]
- Salvage line of the induction treatment with this drug [Initial induction, 1st, 2nd, 3rd or later]
- HSCT before the start of this drug [not performed, performed]
- Pregnancy [absent, present] \* Pregnancy during the treatment period. Limited to cases in which information on pregnancy is collected
- Best overall response [CR or CRi, progression or relapse, indeterminate or other, not performed]
- Best overall response [CR, CRi]\* "Progression", "relapse", "indeterminate/other" and "not performed" are excluded.
- MRD [negativity achieved, negativity not achieved, test not performed] \* Irrespective of the result of best overall response.

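### CR/CRi requires no change from baseline and the effectiveness set has no baseline disease level, so patients with under 5% blasts and no other detectable disease at drug start can be recorded as responders, in numbers no planned summary shows

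*SAP*

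**What the plan says.** Protocol 8.2 takes in every patient given the drug. SAP 5.2 forms the EAS from the safety set by removing cases where effectiveness cannot be properly evaluated (criterion h) and disease other than relapsed or refractory CD22-positive ALL (criterion i). Neither criterion names a blast level.

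Protocol 8.8.11.1 defines CR by conditions that must hold at assessment: "No peripheral blasts or extramedullary disease"; "Trilineage hematopoiesis (TLH) and <5% blasts"; neutrophils above 1,000/μL; platelets above 100,000/μL; and "No recurrence for 4 weeks". CRi prints only a count rule, "Recovery of platelets but <100,000/ μ L or ANC is <1,000/ μ L", and by its name takes the rest from CR. Progressive disease, in contrast, is defined by an increase of at least 25% in blasts or new extramedullary disease.

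SAP 8.2.4.1 sets the analysis: "For patients who achieved the following responses based on the best overall response of hematologic response, their proportion and its confidence interval will be determined". It is run with and without patients who had no response assessment. No analysis is restricted by baseline disease.

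Baseline marrow and peripheral blasts are collected (Protocol 8.8.8). In SAP 5.4 the factor "Myeloblast count immediately before the start of this drug" has the levels ≤50%, >50% and not performed, and peripheral blasts are cut at 1,000/μL. The baseline table in SAP 8.2.2 uses the same cuts.

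**The concern.** Hematologic complete remission is one of the two main efficacy endpoints (Protocol 8.12.2.2). A remission rate is normally read as the share of patients whom treatment brought into remission. Here a patient classed as relapsed or refractory by history, but already below 5% blasts with no other detectable disease at the first dose, satisfies the disease part of the definition before treatment. The 4-week condition tests persistence, not change.

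The same label feeds other outputs: the table of the cycle in which CR/CRi was first reached, MRD and transplant rates among responders (SAP 8.2.4.2 and 8.2.4.3), and survival by best response (SAP 5.4). Baseline marrow blast level is also a named prognostic factor for remission (SAP 6.4). All such patients with a marrow test fall in its ≤50% level, which would favour that level even if blast burden had no influence on response.

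**Working it through.** **The plan's own figures.** The documents give no expected response rate and no precision target for it. The only sample-size calculation concerns VOD/SOS: 176 patients, 18.5% versus 6.2%, two-sided 0.1, power 80.4%. It reproduces (80.2% with the printed rates, 80.4% with 18.45% and 6.15%) and has no bearing here.

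**Reading the text.** Take a patient with 3% marrow blasts, no circulating blasts and no extramedullary disease at the first dose, whose state then does not change.
- Survey entry and EAS: not removed by the printed text if the disease is classed as relapsed or refractory CD22-positive ALL.
- Response: CR if neutrophils and platelets are above the limits and there is no recurrence for 4 weeks; CRi if counts are incomplete.
- Baseline tables and subgroups: shown as marrow ≤50% and peripheral ≤1,000/μL, together with patients who have substantial disease.

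**Size.** Every input below is an assumption.
- f: share of the EAS in this position, 5%, 10% or 20%.
- s: share of them recorded as CR/CRi, 70-90%.
- p: CR/CRi rate in patients with ≥5% blasts, 60%, applied to all remaining patients.
- Share of patients in the ≤50% marrow level: 45%.

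Observed rate = f·s + (1 − f)·p, so inflation = f·(s − p).

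Ratio for ≤50% versus >50%, with a true value of 1.00 in patients with active disease: [f·s + (0.45 − f)·p] / 0.45, divided by p.

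Example, f = 10% and s = 90%: 0.10 × 0.90 + 0.90 × 0.60 = 0.63, which is 3 points above 0.60. Ratio: (0.10 × 0.90 + 0.35 × 0.60) / 0.45 = 0.667; 0.667 / 0.60 = 1.11.

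| f | Inflation, s = 70% | Inflation, s = 90% | Ratio, s = 70% | Ratio, s = 90% |
|---|---|---|---|---|
| 5% | 0.5 points | 1.5 points | 1.02 | 1.06 |
| 10% | 1 point | 3 points | 1.04 | 1.11 |
| 20% | 2 points | 6 points | 1.07 | 1.22 |

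At f = 0 the inflation is zero and the ratio is 1.00. Five points of inflation needs f = 5/30, about 17%, at s = 90%, and is not reached by f = 20% at s = 70%. The result depends on p: letting p run from 40% to 70%, s from 80% to 100% and f from 5% to 20% (illustrative N = 176, whole patients) gives 0.5 to 11.9 points.

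**The case against.** A reader might infer that everyone below 5% marrow blasts at drug start counts as a responder. The documents do not support that. Under 5% is one of several conditions: circulating blasts or extramedullary disease must clear, and CR also needs counts and 4 weeks without recurrence. Such patients can count; they do not automatically count.

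The group may be small or empty. The protocol's relapse category reads "Reappearance of blasts in the blood or bone marrow (>5%) or in any extramedullary site after CR", and a patient below 5% without extramedullary disease does not fit it. That wording is a response category, however, not an entry rule. Criterion h may remove some of these patients. SAP 5.1 and the revision history tie the criteria to a guidance document that is not supplied, so this can be neither confirmed nor excluded.

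A reader might also take f·s as the distortion, for example 7-9 points at f = 10%. That is the rate that would be seen if the drug did nothing. The excess over the rate in patients with active disease is f·(s − p), here 1-3 points. The subgroup ratio would also be hard to tell from chance: 1.11 with an illustrative 79 versus 97 patients has a 95% interval of about 0.89-1.39.

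The data are not hidden. Laboratory values are listed (SAP 9), and further exploratory analyses are allowed (SAP 8.2.4.6). The survey is uncontrolled, mainly about safety, and has no effectiveness hypothesis (SAP 4.1). All of this limits the consequence. It does not supply a planned count or a planned summary.

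Finally, a reader might conclude that the main remission rate should be moved to patients with blasts at baseline. That would not be sound. No baseline extramedullary item appears in Protocol Table 1, 8.8.1 or 8.8.8, so patients with extramedullary disease only, who have real disease to clear, cannot be told apart from patients already in remission.

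**Conclusion.** The gap is in the text and should be closed, but its effect is probably modest and cannot be sized from the documents. Neither the EAS nor the response analysis sets a baseline disease level, CR/CRi requires no change, and no planned summary table shows how many patients had under 5% blasts at the start. With p = 60% and s = 70-90%, the inflation ranges from 0.5 points (f = 5%, s = 70%) to 6 points (f = 20%, s = 90%), and the marrow-factor ratio from 1.02 to 1.22 instead of 1.00. These figures rest on assumed f, s, p and a 45% share in the ≤50% level. They also read the blast criterion as marrow blasts, which its bullet does not say, and assume that criterion h does not already remove these patients. The all-EAS rate should remain the main figure.

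**What to change.** - **SAP 5.4:** split the baseline marrow factor for response, MRD and overall survival as [<5%, ≥5% to ≤50%, >50%, not performed].
- **SAP 8.2.4.1, count:** report the number of EAS patients with <5% marrow blasts and no peripheral blasts at baseline.
- **SAP 8.2.4.1, sensitivity analysis:** beside the unchanged all-EAS figures, give CR/CRi, CR and CRi in EAS patients with baseline marrow blasts ≥5% or peripheral blasts present.
- **Stated limitation:** this subset omits patients with extramedullary disease only, who cannot be identified because no baseline extramedullary item is collected. It also omits patients with no baseline marrow test and no peripheral blasts.
- **SAP 5.2:** if the guidance behind criterion h already excludes patients without evaluable disease, one sentence saying so would settle most of the point.

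Cost: SAP wording and one extra table from data already collected, with a smaller denominator in the sensitivity analysis. SAP version 6.0 already made edits of this kind, adding subgroup categories and changing the response-by-cycle categories. That version (September 2024) postdates the planned database release (May 2024), so the addition should be dated and labelled as a sensitivity analysis.

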##### **8.2.4.2. Minimal residual disease**

For categories based on MRD status, proportions will be calculated according to Section 8.1.2. In addition, patients categorized by the following factor will be analyzed by determining their proportions and

confidence intervals as per Section 8.1.3. Patients who underwent no MRD assessment will also be included in the analysis, but another analysis in patients except them will also be performed.

- Achievement of MRD negativity (achieved, not achieved, not performed)\* Irrespective of the result of best overall response.

Similar analyses will also be performed using the following populations. For the handling of the populations, see Section 8.2.4.1.

- CR or CRi achieved
- CR achieved
- CRi achieved

#### **8.2.4.3. Hematopoietic stem cell transplant**

The proportion of patients who underwent HSCT after the start of this drug and its confidence interval will be determined as per Section 8.1.3. Similar analyses will also be performed using the following populations. See Sections 8.2.4.1 and 8.2.4.2 for the handling of the populations.

- CR or CRi achieved
- MRD negativity achieved
- CR or CRi achieved and MRD negativity achieved
- CR or CRi achieved and MRD negativity not achieved

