8.7. Observation Period

Observation period: The observation period will be 52 weeks for patients not undergoing HSCT within 52 weeks after the start of BESPONSA treatment or until 52 weeks following HSCT for patients undergoing it within 52 weeks after the start of BESPONSA treatment. For a patient starting BESPONSA treatment before 30 April 2020 who is transferred to another hospital during the observation period, the conclusion of the agreement on the implementation of this investigation should be requested to the hospital to which the patient has been transferred, and data from there should be collected to the extent possible.

(1) Treatment phase

From treatment initiation to Day 28 post-treatment: Safety (e.g., AEs) and efficacy (hematologic remission and survival)

(2) Follow-up phase

From Day 29 post-treatment to Week 52 (patients who did not undergo HSCT before Week 52) or 52 weeks after HSCT (patients who underwent HSCT before Week 52): Safety (VOD/SOS) and efficacy (survival)

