8.8.9. Records of investigation discontinuation

For patients who withdraw from the investigation during the observation period, enter the date of discontinuation. For the main reason for discontinuation, i.e., why the investigation cannot be continued, select one of the following options.

(Not making another visit, death, transfer to another hospital or department, or other)

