- White blood cell count immediately before the start of this drug [ $\leq 4000/\text{mm}^3$ ,  $\geq 4000/\text{mm}^3$ , not performed]
- Neutrophil count immediately before the start of this drug [ $\leq 2000/\text{mm}^3$ ,  $\geq 2000/\text{mm}^3$ , not performed]
- Platelet count immediately before the start of this drug [ $< 10 \times 10^4/\mu\text{L}$ ,  $\geq 10 \times 10^4/\mu\text{L}$ , not performed]
- Peripheral blast count immediately before the start of this drug [ $\leq 1000/\mu\text{L}$ ,  $> 1000/\mu\text{L}$ , not performed]
- Myeloblast count immediately before the start of this drug [ $\leq 50\%$ ,  $> 50\%$ , not performed]
- Salvage line of the induction treatment with this drug [Initial induction, 1st, 2nd, 3rd or later]
- HSCT before the start of this drug [not performed, performed]

Subgroup analyses of safety will be performed also for the following factors:

- HSCT after the start of this drug [not performed, performed]
- Type of the first HSCT after the start of this drug [autologous transplant, allogeneic hematopoietic stem cell transplant with myeloablative conditioning, allogeneic hematopoietic stem cell transplant with nonmyeloablative conditioning, unknown]
- Donor of the first HSCT after the start of this drug [alternative donor, matched related donor]
- Conditioning with alkylating agent for the first HSCT after the start of this drug [ $\leq 1$  agent (including no conditioning),  $\geq 2$  agents]
- Conditioning with busulfan for the first HSCT after the start of this drug [not performed (including no conditioning), performed]
- ECOG PS before conditioning for the first HSCT after the start of this drug [0, 1,  $\geq 2$ , not performed]
- AST and ALT levels before conditioning for the first HSCT after the start of this drug [ $\leq 1.5 \times$  the institutional upper limit of normal range (IULN), either  $> 1.5 \times$  IULN, not performed]
- $\gamma$ -GTP level before conditioning for the first HSCT after the start of this drug [ $\leq 50$  IU/L,  $> 50$  IU/L, not performed]

- Total bilirubin level before conditioning for the first HSCT after the start of this drug [≤ institutional upper limit of normal range (IULN), > IULN, not performed]
- Hemoglobin level before conditioning for the first HSCT after the start of this drug [< 10 g/dL, ≥ 10 g/dL, not performed]
- Platelet count before conditioning for the first HSCT after the start of this drug [< 10 × 10^4/µL, ≥ 10 × 10^4/µL, not performed]

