#### 6.2. Effectiveness Endpoints

- Hematologic response. This is assessed as one of the following categories based on the best overall hematologic response: CR, CRi, progressive disease (PD), relapse, indeterminate, other, assessment not performed. "Other" corresponds to the cases where the clinical assessment of hematologic response was performed but the result did not fall into any of the categories described in the case report form, while "assessment not performed" corresponds to the cases where the clinical assessment was not performed.
- MRD. This is assessed as one of the following categories based on the MRD status: negativity achieved, negativity not achieved, unknown, test not performed.
- Overall survival:
  - Overall survival: Defined as the months from the start of this drug to all-cause death.
  - Event: Death
  - Censoring: The patient is confirmed alive at the time of completion or discontinuation of the survey. The endpoint will be censored on the day when patient's survival was last confirmed.
- Overall survival after the final dose of this drug in patients who underwent HSCT:
  - Overall survival: Defined as the months from the date of final dose of this drug to all-cause death.
  - Event: Death
  - Censoring: The patient is confirmed alive at the time of completion or discontinuation of the survey. The endpoint will be censored on the day when patient's survival was last confirmed.

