## 7. HANDLING OF MISSING VALUES

The last observation date is defined as the latest full date among the following:

- Date of administration/discontinuation of this drug

- Date of onset/outcome of adverse event
- Date of assessment of hematologic response
- Date of MRD, laboratory tests, or ECG
- Date of ECOG PS assessment
- Date of hematopoietic stem cell transplant
- Start date of drug therapy or non-drug therapy for the target disease
- Date of survival assessment
- Date of last confirmed survival

If the date of death is missing or partial, it will be imputed based on the date of the last confirmed survival and the last observation date:

- If the date of death is missing, the date of the last confirmed survival will be used. If it is also missing, the last observation date will be used. If the day or month + day of the last confirmed survival is missing, the last observation date or the following date, whichever comes later, will be used.
  - If the day of the date of the last confirmed survival is missing: First day of the month and year when survival was last confirmed.
  - If the month + day of the date of the last confirmed survival are missing: January 1 of the year when survival was last confirmed.
- If the day or month + day of the date of death is missing, the date of the last confirmed survival, the last observation date, or the following date, whichever comes latest, will be used.
  - If the day is missing: First day of the month and year of death.
  - If the month and day are missing: January 1 of the year of death.

If the survival confirmation date is missing or partial, it will be imputed based on the last observation date:

- If the survival confirmation date is missing, the last observation date will be used.
- If the day or month + day of the survival confirmation date is missing, the last observation date or the following date, whichever comes later, will be used:
  - If the day is missing: First day of the month and year of the day of survival confirmation.
  - If the month and day are missing: January 1 of the year of the day of survival confirmation.

If for an adverse event, its seriousness, action made, or outcome is missing, it will be handled as "unknown" when summarizing data.

Cleaning-uncompleted data will be in principle handled as follows.

- Items with missing values: They will be handled as missing (or "unknown" for categorical variables) in both summary and listing.

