#### 8.1.3. Binary variables

For binary variables, patients falling into each binary category will be summarized in terms of frequency (n) and proportion. If a confidence interval (CI) is determined for a proportion, the two-sided 95% CI will be determined using the exact method.

For a comparison of proportion between subgroups, the risk ratio (RR) and its 95% CI will be determined. In addition, the RRs and their 95% CIs will be graphically presented.

For statistical tests, Fisher's exact test will be performed to test correlations in nominal scale data, and Cochran-Armitage test (exact method) to test correlations in ordinal scale data. If, however, it is difficult to use the exact method, chi-square test or Cochran-Armitage test with normal approximation will be used as an alternative to the exact method.

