#### **Continuation/discontinuation of survey (treatment period and follow-up period)**

Definition of the timing 1: < 4 weeks after the start of this drug,  $\geq$  4 weeks to < 8 weeks,  $\geq$  8 weeks to < 12 weeks,  $\geq$  12 weeks to < 16 weeks,  $\geq$  16 weeks to < 20 weeks,  $\geq$  20 weeks to < 24 weeks,  $\geq$  24 weeks to < 52 weeks,  $\geq$  52 weeks, entire period

Definition of the timing 2: < 4 weeks after the end of this drug,  $\geq$  4 weeks to < 12 weeks,  $\geq$  12 weeks to < 24 weeks,  $\geq$  24 weeks to < 48 weeks,  $\geq$  48 weeks, entire period

- Transfer to another hospital**

A patient is defined to have been transferred, if the patient's information at the transferred hospital is linked to the patient's information at the original hospital through the case report form prepared at the transferred hospital. For the SAS and EAS, patients will be summarized by each of the following factors, as per Section 8.1:

- Transfer to another hospital [absent, present]
- Timing of transfer (treatment period, follow-up period) \* The timing will be determined referring to the record of survey continuation/discontinuation in the original hospital's case report form. The denominator will be the number of patients with transfer.

- Summary of excluded patients**

Patients excluded from the SAS, those excluded from the EAS, and reasons for exclusion will be listed.

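### The HSCT proportion in SAP 8.2.4.3 counts patients who leave the survey alive with HSCT status unobserved as not transplanted, so any error is downward

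*SAP*

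**What the plan says.** - **The estimate.** SAP 8.2.4.3: "The proportion of patients who underwent HSCT after the start of this drug and its confidence interval will be determined as per Section 8.1.3". The same is repeated in four populations defined by CR/CRi and MRD status. SAP 8.1.3 supplies the interval: "If a confidence interval (CI) is determined for a proportion, the two-sided 95% CI will be determined using the exact method". The section sets no time horizon, minimum follow-up or censoring rule.
- **The coding.** SAP 5.4 lists "HSCT after the start of this drug [not performed, performed", and SAP 8.2.2 uses the same two levels. By contrast, SAP 6.2 gives MRD the levels "negativity achieved, negativity not achieved, unknown, test not performed".
- **Leaving the survey.** Protocol 8.8.9 lists the reasons for discontinuation: "Not making another visit, death, transfer to another hospital or department, or other".
- **After a transfer.** Under Protocol 8.7 the receiving hospital is asked for its own agreement, and "data from there should be collected to the extent possible". SAP 8.2.1 counts a patient as transferred only "if the patient's information at the transferred hospital is linked to the patient's information at the original hospital".
- **Neighbouring rules.** SAP 6.2 censors overall survival at the last confirmation of survival. SAP 8.1.4 defines cumulative incidence with competing risks, and SAP 8.2.3.3 applies it to deaths after HSCT. Neither is applied to the occurrence of HSCT.

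**The concern.** With two levels and no follow-up condition, someone observed for 52 weeks without a transplant and someone last seen alive at Week 10 without one are counted alike. For the first, *not performed* is an observation. For the second, it means only that no transplant was seen before exit. Transplants that take place after an unlinked exit are lost from the numerator, while the patient remains in the denominator.

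At stake is a planned effectiveness result, overall and in patients with CR/CRi or MRD negativity. Part of what it measures is whether sites keep or link their patients. Its exact interval reflects sampling error only and gives no sign of this.

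**Working it through.** **1. The plan's own figure.** The only design figure is the 80.4% power for the VOD/SOS comparison (Protocol 8.10.2). With 88 per group, two-sided alpha 0.1 and rates of 18.5% and 6.2%, a pooled normal calculation gives 80.2%. With unrounded rates of 18.45% and 6.15% it gives 80.4%. The figure reproduces but has no bearing here. Neither document states an expected HSCT proportion or transfer rate, so every rate below is an assumption.

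**2. Direction.** Let N be the number analysed, x the recorded HSCTs, and L the patients who left alive before Week 52 with no HSCT recorded and no linked record. If u of the L (0 ≤ u ≤ L) are transplanted within the 52 weeks, then

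- reported proportion = x/N
- true proportion = (x+u)/N
- error = −u/N, which lies between −L/N and 0.

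Deaths before HSCT are correctly counted as not transplanted, and linked transfers do not enter L.

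**3. Bounds, with an illustrative x = 70.** N = 176 is the planned safety count; the effectiveness set may be smaller. Reported: 70/176 = 39.8%, exact 95% CI 32.5 to 47.4%.

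| L | L/N | Upper bound (70+L)/176 |
|---|---|---|
| 9 | 5.1% | 44.9% |
| 18 | 10.2% | 50.0% |
| 26 | 14.8% | 54.5% |
| 35 | 19.9% | 59.7% |

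From L = 18 upward, the bound lies above the upper limit of the planned interval.

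**4. Likely size if exit is unrelated to HSCT.** Take constant weekly hazards h (HSCT), d (death without HSCT) and t (unlinked exit) over 52 weeks:

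- true = h/(h+d) × [1 − exp(−52(h+d))]
- recorded = h/(h+d+t) × [1 − exp(−52(h+d+t))]
- share leaving first = t/(h+d+t) × [1 − exp(−52(h+d+t))]

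With h = d = 0.02, true = 0.5 × [1 − exp(−2.08)] = 43.8%. For t = 0.002, recorded = 0.02/0.042 × [1 − exp(−2.184)] = 42.3%.

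| t | Leave first | Recorded | Shortfall (points) |
|---|---|---|---|
| 0.002 | 4.2% | 42.3% | 1.5 |
| 0.004 | 8.2% | 40.8% | 2.9 |
| 0.008 | 15.3% | 38.2% | 5.5 |

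The same t values give 1.1, 2.2 and 4.2 points with h = 0.02, d = 0.03 (true 37.0%), and 1.3, 2.6 and 5.0 points with h = d = 0.03 (true 47.8%).

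**5. Simulation of the first set** (N = 176, 1,000 runs per row, exit as independent censoring).

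| Leave first | Planned proportion, mean | Coverage of planned 95% CI | Leavers dropped, mean | Cumulative incidence, mean |
|---|---|---|---|---|
| 4% | 42.2% | 94% | 44.0% | 43.7% |
| 8% | 40.7% | 88% | 44.3% | 43.5% |
| 15% | 38.4% | 73% | 45.3% | 44.0% |

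Cumulative incidence with death as competing event stays close to the true 43.8%. Dropping the leavers from the denominator overshoots as exit rises.

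**The case against.** **Linkage may be good.** Receiving hospitals must be approached for an agreement. The registration form carries the originating site and patient number. HSCT after drug start is not among the items waived for transferred patients (Protocol 8.8.1, 8.8.2), and Table 1 schedules it in both booklets. The transfer reason also covers a move between departments. All this stands: only unlinked exits matter, and there may be few or none.

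**Existing rules might catch it.** SAP 7 turns missing items into missing or unknown, and EAS criterion h removes patients whose effectiveness cannot be evaluated. The CRF page is not available to check. But the SAP 7 rule addresses missing items in data whose cleaning is incomplete, and a completed entry of no HSCT up to exit is not missing. Criterion h is general. Neither clearly covers the case.

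**The loss will be visible.** SAP 8.2.1 tabulates discontinuation by timing and reason, and follow-up duration by HSCT status. This helps, but reason is not crossed with HSCT status, and the duration table does not separate death from exit alive. L cannot be read from either.

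**It is a descriptive result.** The HSCT proportion is not listed among the endpoints in SAP 6.2 or the main endpoints in Protocol 8.12.2.2, and SAP 4.1 makes all testing exploratory. This limits the importance, not the direction of the error.

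**A stronger reading.** A reader might infer that transplanted patients hidden in the *not performed* group blur the VOD/SOS comparison by HSCT status. The documents do not support that. An unlinked leaver's later VOD/SOS is generally unobserved too, so recorded status matches recorded events. Shorter follow-up would tend to lower the VOD/SOS count in that group and so exaggerate the ratio.

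Nor should these patients be left out of the risk ratios. That would keep deaths and remove survivors in one group only. In an illustration with 45% HSCT among patients fully observed and 5, 10 or 20% leaving early, it would remove 5/57.25, 10/59.5 or 20/64 of the *not performed* group, about 9, 17 or 31%.

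**Conclusion.** The point holds for the HSCT proportion in SAP 8.2.4.3 and its CR/CRi and MRD versions. The plan treats HSCT status unobserved after an unlinked exit as no HSCT, and the error can only be downward. That these patients count as *not performed* follows from the two-level coding and the absence of any other rule; the SAP does not say so in words.

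The size is not derivable from the documents. It is nil if no unlinked leaver is transplanted within the observation period, and at most L/N. With an assumed 4 to 15% leaving early, unrelated to HSCT, it is about 1 to 5 percentage points. A reader might infer a larger shortfall by supposing that sites refer patients elsewhere for transplant, but the documents describe no referral pattern or site transplant capability. This is a modest reporting weakness that is cheap to repair.

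**What to change.** In SAP 8.2.4.3:

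1. Keep the planned proportion and exact interval, but label it *HSCT recorded during the survey*.
2. Beside it, overall and in each CR/CRi and MRD population, report L (left alive before Week 52, no HSCT recorded, no linked record) and the upper bound (x+L)/N.
3. Add the cumulative incidence of first HSCT from drug start to Week 52, with death without HSCT as competing event and censoring at survey exit, by the SAP 8.1.4 method.

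Leave the SAP 5.4 levels and the risk-ratio analyses as they are.

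**Cost:** SAP wording, one count and one further competing-risk run. The dates of HSCT, discontinuation, death and survival confirmation are already collected (Protocol 8.8.5, 8.8.9, 8.8.12).

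**Downside, to be stated with the result:** censoring at exit assumes exit is unrelated to HSCT. If patients are transferred for transplant, the estimate corrects only partly, which is why L and the upper bound belong beside it.
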